#### 3 STUDY DESIGN

This is a multi-site, two stage, open label, randomized (1:1:1) controlled trial.

Figure 2. Schematic of study design

Treatment is for 14 days from baseline. Patients will receive follow-up assessment at 7, 14 and 28 days after the first dose.

The time allowed for screening assessments allows time for eligibility assessments to be included.

- Screening Period: up to 7 days to the day randomisation
- Treatment Period: 14 days

MATIS version 4.0 dated 2nd November 2022

IRAS: 282552 Page **22** of **57** 

Imperial College Healthcare

- Follow-up period: Day 14 to 28

Patients who have recovered and are fit for discharged from hospital during the treatment period, will be discharged home with trial medication to complete a fixed 14 day course. Such patients will be followed up weekly with telephone monitoring until day 28 and additional blood test monitoring where practically possible.

#### 3.1 SAMPLE SIZE

171 (57 per arm) patients with COVID-19 pneumonia will be recruited to Stage 1, if the trial progresses to Stage 2 an additional maximum of 285 (95 per arm) will be recruited, resulting in a potential sample size of 456 if three trial arms continue for the whole trial (152 per arm). These numbers have been chosen to provide a power of 90% with a maximum 5% chance of an intervention arm being recommended when it provides no improvement over control (5% one-sided family-wise error rate).

Patients will be enrolled into RUX, FOS or SOC groups, as shown in the flow chart.

#### 3.2 STUDY SITES

The trial will commence at one site, Imperial College Healthcare NHS Trust in the UK, with further UK based sites that will include Reading, Hillingdon, London North West University Healthcare NHS Trust (Northwick Park Hospital and Ealing Hospital), Leeds and Sheffield Teaching Hospitals NHS Foundation Trust.

#### 3.3 STUDY ENDPOINTS

#### **Primary endpoints**

The primary endpoint is progression from mild to severe COVID-19 pneumonia within 14 days in hospitalised patients. Patients are recruited at a WHO COVID-19 Severity Score of 3 and 4 and the primary endpoint is the comparison of patients whose COVID-19 pneumonia progresses to a severity score  $\geq$  5 on the modified WHO Ordinal Scale. Specifically, the primary endpoint is met when the following are recorded within 14 days:

- Death
- Requirement for invasive ventilation
- Requirement for non-invasive ventilation including CPAP and high flow nasal oxygen
- O2 saturation < 90% on ≥60% inspired oxygen

#### **Secondary endpoints**

Comparison of the incidence, time-to-event, median or odds ratio of each of the parameters below at 14 and 28 days between RUX or FOS versus SOC:

- Mortality
- Invasive ventilation
- Non-invasive ventilation including CPAP and high flow nasal oxygen
- Renal replacement therapy
- Venous thromboembolism
- Inflammatory markers CRP, LDH, ferritin, D-dimer
- Serum creatinine
- Length of stay
- SSARs and discontinuations of study arms
- Change in severity on the modified WHO COVID-19 Ordinal Scale

Comparison of the incidence, time-to-event, median or odds ratio of each of the parameters below:

- Mortality at 3, 6, 12 & long term outcome
- Venous thromboembolism rate at 6, 12 and 18 months
- Renal replacement therapy at 6, 12 and 18 months
- Occurrence of new hypertension diagnosis
- Occurrence of new diabetes diagnosis
- Number of re-admissions within 12 months
- Causes of re-admissions in the last 12 months
- Occurrence of lung fibrosis
- Co-morbidities developed within 18 months post-discharge from hospital

Further secondary and exploratory objectives are not the focus of this study but maybe adopted using routine healthcare records (e.g. NHS Digital) and relevant research studies (e.g. UK Biobank and Genomics England). This will allow subsidiary analyses of the effect of the study treatments on particular non-fatal events (e.g. ascertained through linkage to Hospital Episode Statistics), the influence of pre-existing major co-morbidity (e.g. chronic heart, lung, kidney, liver disease, diabetes and use of immunosuppressive drugs) and longer-term outcomes (e.g. 6 month survival) as well as in particular sub-categories of patient (e.g. by genotype).

#### **Exploratory endpoints**

MATIS version 4.0 dated 2nd November 2022

IRAS: 282552 Page **24** of **57** 

Imperial College Healthcare

Blood samples will be taken as per protocol schedule to evaluate changes in immune cells and platelets over time to look for biomarkers to predict response. This will include fresh blood analysis, and collecting DNA, plasma, serum and PBMCs for freezing and future analysis. Samples will be stored under Imperial College Tissue Bank.

#### 3.4 LONG COVID FOLLOW UP SUB-STUDY

The LONG COVID sub-study is a prospective cohort study. The aim of the study is to assess the long term effects of COVID-19 infection in patients who were mild-moderately affected and hospitalised due to a COVID-19 infection and to assess the impact of signal inhibitors on the development of PACS. Patients with PACS are defined as those who have had the following symptoms >12 weeks post COVID-19 infection with no alternative diagnosis:

- Persistent fatigue
- Shortness of breath
- Decline in Quality of Life
- Persistent cough
- Cognitive disturbance (brain fog)
- Thromboembolism (spontaneous)
- Chronic kidney disease (post covid-19)

Participants approached and randomised for the study will also be approached to participate in the sub-study. All participants enrolled into the main study will be eligible for the PACs sub-study. This study is covered in a separate patient information sheet and informed consent form.

Data will be collected up to 18 months post-consent of the main study will be collection from participants, and, where appropriate, legal representatives who have provided informed consent (where relevant). Participant's general practitioners and local health authorities may also be contacted in order to obtain further data regarding the participant's health during the 18 month follow up period. Data will include clinical and treatment data regarding the long term effect of COVID-19 on participants' health; and other data of relevance to their health will be collected from participants via phone and electronic medical records.

IRAS: 282552 Page **25** of **57** 

Imperial College Healthcare

Participants will be asked to either consent via telephone with their local PI or person delegated within the study team or in person on site.

For telephone consenting, the PIS will be sent to already recruited participants in the main study before following up with a call explaining the substudy and asking for consent. We will request confirmation of who they are (full name and date of birth), explain that the call is regarding MATIS study and ask that they clarify this in order to ensure correct person identification whilst not revealing any personal information.

When all confirmed the study will be explained according to the PIS previously sent to them.

Telephone consent will be obtained in which on the consent form it is clearly stated that a conversation is had with the patient and the researcher initials the boxes that the patient has verbally declared participation.

#### 4 STATISTICS AND DATA ANALYSIS

#### 4.1 DATA ANALYSIS

The aim of the trial (stage 1 and 2) is to test whether RUX and FOS (separately) provide significant improvement in primary outcome compared to SOC. To do this we will test the two null hypotheses and provide estimated treatment effect (ORs) with 95% confidence intervals (CIs).

#### Interim analysis (Stage 1)

The aim of the Stage 1 interim analysis is to provide an opportunity to stop enrolling patients to an intervention arm that is not showing sufficient promise of efficacy. The Stage 1 review will be undertaken by a statistician that is independent of ICTU and overseen by the data monitoring committee who will advise on whether the trial should continue with both intervention arms, with one intervention arm, or stop at this stage. This decision will be based on a suggested one-sided p<0.25 although interpretation of the p-value will be on the continuous scale as strength against the null hypotheses and will not be restricted to a single binary threshold. Our sample size calculations for both stages ensure we have a good prospect of these achieving these aims.

Current rate of severe pneumonia in the standard of care is 50%. In the case that an experimental arm reduces this to 30% (relative risk, RR, 0.6), then the design provides a 92% chance (one sided alpha 0.25) of it being recommended to continue to stage 2.

#### Full trial (Stage 2)

If the trial is recommended to continue at Stage 2 based on DMC interim review the full trial will need to recruit an additional 95 for each arm that continues (152 per arm in total; 456 to the complete trial). This will provide 90% power to detect a change of RR of 0.6 (50% to 30%), with one-sided alpha of 0.027 (5% FWER) and has been inflated for 5% for missing outcome data. Here the power is the chance of an effective treatment passing stage 1 and being recommended after stage 2. The design recommends stopping an intervention arm at stage 1 if the one-sided p-value is >0.25. The above power assumes this rule is always followed and the FWER assumes it is not followed (hence the actual FWER will be lower if the rule is always followed).

#### 4.2 STATISTICAL ANALYSIS PLAN

Analysis will be on an intention to treat (ITT) population including all randomized patients, multiple imputation will be used to include participants who have missing outcome data. Comparisons for efficacy will be made between all participants randomised to the different treatment arms, irrespective of whether they received their allocated treatment ("ITT" analyses). Comparisons for safety will be made between all participants randomised to the different treatment arms who have received at least one dose of study medication. Multiple imputation makes a missing at random assumption and a sensitivity analysis around the assumptions made will be performed using controlled multiple imputation that permits exploration of a not missing at random assumption. A complete case analysis will also be performed. The primary outcome will be analysed as binary with participants categorised WHO COVID-19 Ordinal Score <5/  $\ge 5$  by 14 days.

For Stage 1 analysis (after a target recruitment of 171 participants) we will calculate the Wald test statistics from separate logistic regression models for RUX vs SOC and FOS vs SOC, adjusted for stratification variables, with 95% confidence intervals and p-values. P-values will be one-sided and judged at the 0.25 level.

If at least one intervention arm shows promise, then stage 2 will recruit a further 95 per arm (the maximum combined sample size of stages 1 and 2 is 456 patients). The stage 2 analysis will use a one-sided p-value

MATIS version 4.0 dated 2nd November 2022

IRAS: 282552 Page **27** of **57** 

threshold of 0.027. This has been chosen to control the maximum chance of recommending an ineffective treatment at 0.05.

Contamination is a potential threat in many C19 trials, as standard of care is continuously evolving, and coenrolment to ongoing trials present a real challenge if unequal enrolment occurs across arms. For participants who were co-enrolled to a trial at the same time, or prior to the randomisation to this trial, we will adjust the final analysis though covariate adjustment. For participants who were subsequently co-enrolled after randomisation, we treat this as a post-randomisation variable and undertake a supplementary analysis to adjust for this variable along with the receipt of post-randomisation rescue medication.

In Stage 2 a logistic regression model will be used to assess the treatment effect of RUX and FOS compared to SOC. The model will include the treatment arms, baseline modified WHO Severity Score, trial co-enrolment at baseline, and randomisation stratification variables viz. site and age (<65 vs ≥65). As well as reporting OR and 95% CIs, the model will be used to estimate the difference in proportion of participants with modified WHO COVID-19 Ordinal Score ≥5. The treatment effect in the absence of post-randomisation co-enrolment and receipt of rescue medication will be estimated in a supplementary analysis where participants' outcomes after either will be treated as missing and a controlled multiple imputation using a delta based approach will be used.

For the primary outcome, progression to severe COVID-19 disease within 14 days, discharge alive from the admitting hospital before 14 days will assume safety from the event (in the absence of additional data confirming otherwise). An additional sensitivity analysis will be performed if there is a change of dose after review of the first thirty patients.

For time-to-event analyses required for secondary endpoints such as time to discharge, each treatment group will be compared with SOC and modelled using a proportional hazards time-to-event model adjusted for randomisation stratification variables. Kaplan-Meier estimates for the time to event will also be plotted (with confidence intervals). The log-rank 'observed minus expected' statistic (and its variance) will be used to estimate the average event rate ratio (and its confidence interval) for those allocated to each treatment group versus the no additional treatment group.

Pre-specified subgroup analysis will be conducted for the primary outcome using the statistical test for interaction (or test for trend where appropriate) for the following: disease severity as graded by the WHO

MATIS version 4.0 dated 2nd November 2022

IRAS: 282552 Page **28** of **57** 

Imperial College Healthcare

COVID-19 Ordinal Severity Scale; time since onset of symptoms; sex; age; and comorbidities obesity, chronic heart, lung, kidney and liver disease, diabetes, immunocompromised and smoking status. Pre-specified subgroup analyses will also be conducted for the primary outcome using the statistical test for interaction (or test for trend where appropriate) for patients with admission CRP >200mg/L and/or D-dimer 2500ng/mL.

Further details will be fully described in the Statistical Analysis Plan (SAP).

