The stage two primary analysis will consist of fitting one binomial regression model regardless of whether one or two experimental treatments progress from stage one. Specifically a generalized linear model with WHO COVID-19 status (<5 or \ge 5) as the outcome and treatment group, baseline WHO COVID-19 score (3 or 4), age (<65 or \ge 65), receipt of known effective treatments dexamethasone and/or tociluzimab, prior vaccination against COVID-19 (y/n) and receipt of paxlovid and/or molnupiravir at the time of or prior to randomisation into MATIS as covariates will be fitted. Effective treatments will be included as separate covariates in the primary analysis model. Given the anticipated small number of sites in this study, site will also be included in the model as a fixed effect. In the event that all participants are on one of the effective treatments that covariate will be removed from the model.

If including site as a fixed effect results in unstable model estimates e.g. if there are a number of sites with very few randomisations we will exclude site from the model and we will only adjust for baseline WHO COVID score, age group, receipt of known effective treatments dexamethasone and/or tociluzimab, prior vaccination against COVID-19, and receipt of paxlovid and/or molnupiravir.⁶ We will also consider not adjusting for paxlovid and/or molnupiravir if the number of participants receiving these are low. If after removing sites and treatments the model is not stable due to event rate:covariate ratio we will adjust for all covariates using a propensity score approach.

The model will be fitted with a binomial distribution and logit link function and the treatment effect will be reported as an odds ratio with corresponding 95% confidence interval and p-values. P-values will be one-sided and judged at the 0.027 level. Therefore, a two-sided p-value < 0.054 will be used to indicate a significant treatment effect.

The stage two model to be fitted to estimate the treatment effects will be:

$$logit(\pi_{ij}) = \beta_{0} + \beta_{1}RUX_{ij} + \beta_{2}FOS_{ij} + \beta_{3}WHO_{ij}^{0} + \beta_{4}AGE_{ij}^{0} + \beta_{5}DEX_{ij}^{0} + \beta_{6}TOC_{ij}^{0} + \beta_{7}VAC_{ij}^{0} + \beta_{8}PAX_{ij}^{0} + \beta_{9}MOL_{ij}^{0} + \beta_{10}SITE_{1} + \beta_{11}SITE_{2} + \cdots + \beta_{12}SITE_{i-1}$$

 RUX_{ij} : dummy variable for treatment ($RUX_{ij} = 0$ or 1) for participant i in jth site

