3.1.5 Stage 2 exploratory analysis for primary outcome

i. Co-enrolment at time of randomisation

An exploratory analysis of the primary outcome will be undertaken in order to assess the impact of co-enrolment to an 'active'* arm of another study at the time of or prior to randomisation into MATIS (includes day of randomisation or one day post randomisation). Individual treatments will be included as separate covariates in the primary analysis model described above. In the event of low event rates the sensitivity analysis will be repeated removing one covariate at a time.

*We will only consider those co-enrolled to an 'active' arm of another study. Co-enrolment to the standard of care arm in other studies will not be considered an active treatment.

ii. Co-enrolment post randomisation and receipt of rescue medication

We will explore what the direct effect of the treatment is on the outcome, and whether there is an indirect effect of receipt of active treatment as a result of co-enrolment when occurring post-randomisation, and receipt of known effective treatments dexamethasone, tociluzimab, paxlovid and molnupiravir post-randomisation (>1 day post randomisation). Where post-randomisation co-enrolment or receipt of known effective treatments must occur prior to the occurrence of the outcome. We will do this via a mediation analysis using a structural equation modelling approach using the Stata *paramed* command.^{7, 8}

The analysis will allow us to decompose the total observed treatment effect into mediated (indirect, described by the natural indirect effect in the Stata output) and non-mediated (direct, described by the natural direct (and controlled direct effect) effect estimate in Stata output) components. Each post-randomisation active intervention and known effective treatments will be treated as an individual mediator, thus we will estimate the mediated effect separately for each. Analysis models will adjust for baseline WHO COVID-19 score (3 or 4), age (<65 or ≥65), receipt of known effective treatments dexamethasone and/or tociluzimab, prior vaccination against COVID-19, and receipt of paxlovid and/or molnupiravir at the time of or prior to randomisation into MATIS and site as fixed as per the primary analysis model described in section 3.1.3. The model will be modified in a similar manner as the primary outcome modelling in the event of low event rates.

iii. Compliance

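### Protocol 4.2 and SAP 3.1.3 list different covariates for the single confirmatory Stage 2 model: baseline trial co-enrolment is in the protocol's model but only exploratory in the SAP

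*Protocol*

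**What the plan says.** Protocol 4.2 presents the issue as a risk to the trial: "Contamination is a potential threat in many C19 trials, as standard of care is continuously evolving". It names unequal co-enrolment across arms as the other route. For patients who joined another trial at the same time as this one, or "prior to the randomisation to this trial, we will adjust the final analysis though covariate adjustment". It then sets out the Stage 2 logistic regression: "The model will include the treatment arms, baseline modified WHO Severity Score, trial co-enrolment at baseline", plus the stratification factors site and age group. Co-enrolment after randomisation goes to a supplementary analysis.

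SAP 3.1.3 builds the Stage 2 primary model from treatment group, baseline WHO score, age group, "receipt of known effective treatments dexamethasone and/or tociluzimab, prior vaccination against COVID-19 (y/n) and receipt of paxlovid and/or molnupiravir", and site. It adds: "Effective treatments will be included as separate covariates in the primary analysis model". Baseline co-enrolment is absent from the text, the equation and the variable definitions. The imputation model (SAP 3.1.2, extended in 3.1.3) has a variable for effective treatment received through later co-enrolment, but none for co-enrolment at baseline.

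SAP 3.1.5 i gives baseline co-enrolment its only inferential role: "An exploratory analysis of the primary outcome will be undertaken in order to assess the impact of co-enrolment", coded treatment by treatment and counting only allocation to an active arm elsewhere. On control-arm patients it says: "Co-enrolment to the standard of care arm in other studies will not be considered an active treatment".

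Both documents judge the Stage 2 result at one-sided 0.027.

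**The concern.** A confirmatory test needs one model. Here two are specified for the same outcome, patients and threshold. They will generally give different odds ratios and p-values, and near 0.027 the choice between them can decide the result. A choice made after unblinding would be hard to defend.

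The protocol also names co-enrolment as a threat and commits the final analysis to adjusting for it, yet the SAP's main estimate does not carry that adjustment. The exploratory analysis does not replace it. It ignores co-enrolment to control arms, it counts co-enrolment up to one day after randomisation in an open-label trial, and its result does not bear on the 0.027 decision.

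**Working it through.** **1. The two covariate lists**

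| Term | Protocol 4.2 | SAP 3.1.3 |
|---|---|---|
| Treatment, baseline WHO score, age group, site | yes | yes |
| Trial co-enrolment at baseline | yes | no (exploratory, 3.1.5 i) |
| Dexamethasone, tocilizumab, vaccination, paxlovid, molnupiravir | no | yes (five terms) |

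The lists differ in both directions. Adding co-enrolment to the SAP alone would still leave two different models.

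**2. Does anything settle it?** Protocol 4.2 leaves further details to the SAP, which does not amount to replacing a listed covariate. The SAP says it rests on protocol version 2.2, and version 4.0 still carries the co-enrolment term. The amendment log describes versions 3.0 and 4.0 as sub-study, biomarker and consent changes, with no change to the model. Neither document has a precedence clause.

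**3. The plan's own figures.** Inputs from Protocol 4.1: 50% versus 30%, 57 then 152 per arm, one-sided 0.25 then 0.027. Power at each stage is Φ[(0.20 − z·√(0.48/n)) / √(0.46/n)].
- Stage 1, n = 57: 0.938 (plan: 92%).
- Stage 2 alone, n = 152: 0.952.
- Both stages, bivariate normal with correlation √(57/152) = 0.612: 0.908 (plan: 90%). With 5% loss (54 and 144 per arm): 0.894.
- Family-wise error for two arms sharing a control (correlation 0.5) at 0.027: 0.0489 (plan: 5%).

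The design figures reproduce. They do not depend on the covariate question.

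**4. Overall error and power with and without the term.** Co-enrolment prevalence and effect are not in the documents. Assumed: prevalence 10% or 30%, odds ratio (OR) for progression 0.3, 0.5 or 0.7, same prevalence in both arms, 144 per arm, 4,000 simulated trials per setting, model with treatment only or treatment plus co-enrolment.
- One-sided type I error: 0.021 to 0.030 without the term, 0.020 to 0.031 with it (simulation SE √(0.027 × 0.973/4000) ≈ 0.0026).
- Final-stage power at 50% versus 30%: 0.935 to 0.949 without, 0.936 to 0.955 with.

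**5. Error when chance has favoured the experimental arm.** Same simulation with no treatment effect. Prevalence is 20% on SOC and higher on the experimental arm, standing in for a chance imbalance of that average size.

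| Experimental-arm prevalence | Co-enrolment OR | Error without term | Error with term |
|---|---|---|---|
| 25% | 0.5 | 0.032 | 0.024 |
| 25% | 0.3 | 0.040 | 0.026 |
| 30% | 0.5 | 0.048 | 0.0245 |
| 30% | 0.3 | 0.075 | 0.026 |

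The SD of the difference at 20% prevalence is √(2 × 0.2 × 0.8/144) = 0.047, so 5 points is about 1.1 SD and 10 points about 2.1 SD.

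Shift in the estimate at 152 per arm and 30% prevalence: SD = √(2 × 0.3 × 0.7/152) = 0.053, and 1.96 SD = 0.103. The log OR moves by about 0.103 × ln 0.5 = −0.071 (factor 0.93), or 0.103 × ln 0.7 = −0.037 (factor 0.96), that is 4% to 7%.

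**6. How often the verdict changes.** Models with WHO grade and age, with and without co-enrolment (prevalence 30% or 50%, OR 0.4 to 0.6, 144 per arm, 5,000 trials per setting). The two disagree at 0.027 in 1.1% to 1.8% of trials at 50% versus 30%, and in 3.4% to 5.8% at an assumed smaller effect of 50% versus 36%. A second run (3,000 trials, its own assumed grade and age effects) gave 0.8% to 1.8% and 3.8% to 6.7%.

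**The case against.** The strongest reply is that the SAP's model is clear in itself: one equation is labelled primary, and co-enrolment is labelled exploratory. It adjusts for four named drugs at baseline by whatever route they were given, and for vaccination. That deals directly with the evolving standard of care the protocol worries about, and arguably better than a bare co-enrolment flag. The SAP's active-arm, per-treatment coding is also defensible, since a single flag pools active and control patients from unlike trials. Most of this stands. It does not remove the conflict with the protocol or cover other agents received through co-enrolment.

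The simulated effects are also open to challenge. They add one term to a small model, whereas the relevant effect is what remains after the SAP's five extra terms. With 30% prevalence and 4,000 trials, a pure-noise covariate (OR 1.0) already gives discordant verdicts in 0.4% of trials at 50% versus 30% and 1.3% at 50% versus 36%. A residual OR of 0.8 gives 0.4% and 1.6%, hardly different from noise. The 4% to 7% shift is, by construction, the size of a 1-in-20 imbalance. This stands, and the numerical effect should be called small.

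A reader might infer that the protocol prescribes a yes/no indicator for interventional trials. It does not: Protocol 4.2 gives no coding. Nor do the documents say that any co-enrolling study is blinded, so an argument that active-arm status would be unknown rests on an assumption.

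**Conclusion.** The conflict is certain from the text: one confirmatory test, two covariate lists, no stated reason and no rule for which decides at 0.027.

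Two stronger conclusions are tempting and not supported. One is that protection against contamination is absent from the main result. It is only partly absent, because the SAP adjusts for the four drugs and vaccination; the gap is other agents received through baseline co-enrolment. The other is that the trial's type I error is inflated. Co-enrolment before randomisation can differ between arms only by chance, and step 4 shows no inflation beyond simulation error. Co-enrolment after randomisation is a separate matter, which both documents keep outside the primary model.

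What remains is conditional error under unlucky imbalance (0.032 to 0.075 without the term against about 0.025 with it, for differences of 5 to 10 points and ORs of 0.3 to 0.5), a small loss of precision, and freedom to choose between models. All these sizes rest on assumed prevalences and effects and leave out the SAP's treatment terms, so the real effect is likely small. The effect of those five terms on the gap between the two documents' models was not computed. The point merits correction because the specification is unsettled and cheap to settle.

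**What to change.** Before unblinding, agree one covariate list for the Stage 2 model and state it identically in Protocol 4.2 and SAP 3.1.3.

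- **Preferred:** add a defined baseline co-enrolment term, at or before randomisation, to the SAP 3.1.3 model and its imputation model. State whether it means any co-enrolment or active arms only. Extend the low-number fallback in SAP 3.1.3, which names site, paxlovid and molnupiravir, to name this term. Amend Protocol 4.2 to list the SAP's treatment and vaccination covariates.
- **Alternative:** amend Protocol 4.2 to match SAP 3.1.3, with a stated reason for moving co-enrolment to exploratory status.

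Either way, keep the per-treatment active-arm analysis in SAP 3.1.5 i as exploratory.

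The preferred route costs one degree of freedom and a short edit to each document. Co-enrolment is already due to be summarised at both stages (SAP 2.3). The alternative costs a protocol edit and leaves the remaining gap in adjustment, but openly.
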